# Study Protocol

---

## Study design

This research will comprise two complementary studies to obtain direct and indirect measures of the effects of running on knee cartilage in people with and without TFOA. Biomechanical outcomes will be collected *during* running, while cartilage outcomes will be assessed *before and after* running on a separate day. Comparisons between groups will be made prior to starting a 12-week running intervention (baseline), as well as upon completion (follow-up).

## Participants

Two distinct groups will be recruited. All eligible participants will be: (i) aged greater than 40 years; (ii) recreational runners who run at least twice per week for a total of at least 10km, and have done so for a minimum of 12 months; and (iii) be comfortable running on a treadmill for 30 minutes. Participants in the TFOA Group will: (i) exhibit radiographic evidence of mild or moderate TFOA according to the Kellgren and Lawrence (KL) OA classification scale (presence of osteophytes and joint space narrowing on X-ray; grades 2 and 3); and (ii) report knee pain on most days of the previous three months (not just during running). Runners in the Control Group will: (i) be free of any radiographic signs of TFOA according to the KL scale (an absence of definitive osteophytes and joint space narrowing; grade 0 – note that we will not be recruiting KL grade 1 individuals due to the potential for early osteoarthritic changes in these individuals); and (ii) be pain-free in both knees for the 12 months prior to recruitment.

Exclusion criteria for both groups will be: (i) any history of traumatic knee injury (defined as one that required surgical intervention or continuous treatment for more than one month); (ii) presence of an inflammatory arthritic condition; (iii) presence of any health condition (other than OA in the TFOA group) affecting normal movement or that precludes engaging in moderate to high impact activities such as running; (iv) use of any oral or injected corticosteroids or viscosupplementation in the previous six months; and (v) any history of surgery in either knee. Furthermore, standard contra-indications to MRI will be assessed for safety purposes.

A total of 80 individuals will be recruited for this study: 40 in each group. Groups will be matched for sex, age (+/- 2 years), body mass (+/- 5 kg), and running experience (+/- 1 year). We are unaware of any studies directly relevant to our proposal that would appropriately inform a sample size calculation. Instead, four similar studies have quantified T2 and T1p under loading conditions: Mosher *et al.* 2010, Subburaj *et al.* 2012, and Gatti *et al.* 2017 employed running protocols, but in 37, 20, and 15 young, healthy individuals only; Souza *et al.* 2014 used a lower limb weighting paradigm in a supine position enrolling 44 individuals with knee OA. Thus, our proposed sample of 40 individuals per group is consistent with – and in most cases, exceeds – these studies, and reflects a feasible number within the 5-year timeline proposed for this research.

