Official Title: Linking Biomechanical and Imaging Outcomes to Better Understand the Effects of Running on Knee Joint Health

NCT Number: to be assigned

Document Date: 30-11-2019

Statistical Analysis Plan

All data will be analyzed by our statistician, who will remain independent of all data collection and analyses. Means and standard deviations will be calculated for all outcomes. One factor ANCOVAs will be used to assess between-group differences in running biomechanics outcomes at each biomechanics testing session. At each individual MRI testing session, two factor (group x scan time) repeated measures analyses of covariance (ANCOVAs) will be conducted to examine differences between groups, changes across the MRI scan times (pre-run, immediate-post, 45-minute-post), and any interactions present. Finally, two-factor (group x time) ANCOVAs will be conducted to assess the longer-term effects of the running intervention on biomechanical and MRI outcomes. Treadmill running speed will be a covariate in all statistical analyses, while running mileage during the course of the intervention (defined as % change from baseline) and peak vertical loading rate during the associated biomechanical testing will be additional covariates for MRI outcome changes. To account for the exploratory nature of this research, a significance level of $p = 0.05$ will be used, and no corrections for multiple comparisons will be used. Finally, an exploratory sex-based, sub-group analysis will be conducted to help inform future studies in this area.

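### The ANCOVAs leave out all four matching variables, so standard errors for between-group level comparisons are too wide if those variables predict the outcome, and one-sided imbalance within the calipers goes unadjusted

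*Protocol*

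**What the plan says.** The Participants section of the protocol sets the size of the study, "A total of 80 individuals will be recruited for this study: 40 in each group", and then the matching: "Groups will be matched for sex, age (+/- 2 years), body mass (+/- 5 kg), and running experience (+/- 1 year". It does not say whether this means individual pairs or similar group averages. It gives no power calculation: "We are unaware of any studies directly relevant to our proposal that would appropriately inform a sample size calculation".

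Level comparisons between the groups are a stated aim under Study design: "Comparisons between groups will be made prior to starting a 12-week running intervention (baseline), as well as upon completion (follow-up".

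The SAP plans three families of model:
- For biomechanics: "One factor ANCOVAs will be used to assess between-group differences in running biomechanics outcomes at each biomechanics testing session".
- For MRI at each session: a repeated measures ANCOVA with group and scan time as factors.
- For longer-term effects: an ANCOVA with group and time as factors.

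On covariates it says "Treadmill running speed will be a covariate in all statistical analyses". For changes in MRI outcomes it adds "running mileage during the course of the intervention (defined as % change from baseline) and peak vertical loading rate during the associated biomechanical testing". The only matching variable that reappears is sex, and only in this form: "an exploratory sex-based, sub-group analysis will be conducted to help inform future studies in this area". No model has a pair or matched-set term, and no other text in either document adds one.

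**The concern.** Matching at recruitment makes the groups alike on the four variables, but it does not remove the effect of those variables on the outcome. Older or heavier runners may still differ from younger or lighter ones within each group, and a model without these variables counts that spread as error. The group difference then varies less from sample to sample than the model assumes, so the reported standard error is too large.

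Two things are at stake. The first is power: a study of 40 per group, sized by precedent and feasibility, could miss group differences although the variables that would sharpen the comparison are already in hand. The second is residual imbalance: the calipers limit how far apart the groups may be but do not require the differences to average to zero. If one group tended to be older, heavier or more experienced within the permitted range, the planned models would not correct for it.

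The comparisons exposed are those of level: the biomechanics comparison at each session and the group main effect for MRI.

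**Working it through.** **Inputs from the documents.** n = 40 per group; calipers of 2 years, 5 kg and 1 year, with sex matched exactly; significance level 0.05 (taken as two-sided, since the SAP does not say); speed as the covariate common to all models. The plan has no power figure to reproduce; the only arithmetic is 2 x 40 = 80.

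**Assumptions.** R2 is the share of outcome variance, after speed, that the four variables explain; values 0, 0.1, 0.2 and 0.3 are used. The group difference for power is 0.5 SD. None of these is in the documents.

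**Step 1, reported standard error and equivalent sample size.** The ratio of the planned to the adjusted standard error is 1/sqrt(1 - R2). The planned model would need 40/(1 - R2) per group to match the adjusted interval width.

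**Step 2, power from the noncentral t.** The per-session model with intercept, group and speed has 80 - 3 = 77 residual degrees of freedom; four more covariates leave 73. The noncentrality is 0.5 x sqrt(20) = 2.236 for the planned model and 2.236/sqrt(1 - R2) for the adjusted one.

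| R2 | SE ratio | Equivalent n per group | Power, planned | Power, adjusted |
|---|---|---|---|---|
| 0 | 1.000 | 40 | 59.8% | 59.7% |
| 0.1 | 1.054 | 44.4 | about 60% | 64.3% |
| 0.2 | 1.118 | 50 | about 60% | 69.4% |
| 0.3 | 1.195 | 57.1 | about 60% | 75.1% |

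Planned power hardly moves with R2 because the planned standard error does not respond to it. Simulations under both forms of matching gave 58.5% to 60.9%.

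**Step 3, balanced differences within the calipers.** Simulated pairs had the same sex and differences uniform on either side of zero. The four variables had equal weight, with assumed SDs for age, mass and experience of 6/10/6, 8/12/8 or 5/8/3. At R2 = 0.3 the planned model's mean reported standard error was about 0.225, against a true sampling SD of about 0.19. The planned test rejected a true null about 2% of the time at R2 = 0.3 and about 4% at R2 = 0.1. The adjusted model stayed near 5%. If only group means are held within the calipers, the planned test is less conservative (roughly 3% at R2 = 0.3).

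**Step 4, one-sided differences within the calipers.** Now let one group always be on the higher side, with differences uniform from 0 to the caliper. The mean differences are 1 year, 2.5 kg and 0.5 year. With equal weights, each standardised variable has coefficient sqrt(0.3)/2 = 0.274 at R2 = 0.3.
- SDs 8/12/8: (0.125 + 0.208 + 0.063) x 0.274 = 0.11 SD bias.
- SDs 6/10/6: (0.167 + 0.250 + 0.083) x 0.274 = 0.14 SD bias.
- SDs 5/8/3: (0.200 + 0.313 + 0.167) x 0.274 = 0.19 SD bias.

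In simulation the planned test then rejected a true null about 4% to 9% of the time at R2 = 0.3, depending on the SD set. Adding the four covariates removed the bias and returned the rate to about 5%.

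**Step 5, overlap with speed.** If speed correlates 0.5 with the combined matching score at R2 = 0.3 (here the total share, before speed), planned power rises to 64% and adjusted power is 74%. The gap falls from 14 points (61% against 75% in the same simulation without correlation) to 10.

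**The case against.** The strongest case against the point has four parts.

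*Every size is assumed.* This stands. The documents give no R2, outcome SD or effect size. At R2 = 0 nothing is lost, and at R2 = 0.1 the gain is about 4 points of power. The choice to match suggests that the variables were thought relevant, but it does not establish that they predict these outcomes.

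*The scope is narrow.* This also stands. Contrasts between scan times, or between baseline and follow-up, already remove stable participant effects. Interactions with group suffer only if the four variables predict change.

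*Planned covariates absorb some of it.* This stands in part. Speed, and loading rate where it is used, recover whatever they share with the matching variables; Step 5 shows a smaller but still material gap.

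*The study is exploratory and matching already deals with comparability.* Adjustment is indeed optional here. But an avoidably conservative test sits badly with a plan that gives up multiplicity correction for the sake of exploration.

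Three stronger readings are tempting and are not supported. A reader might infer that the planned analysis is always conservative, and therefore safe. That needs differences within the calipers to balance out, which the protocol does not require. A reader might infer the opposite, that the group comparison is biased. That needs one-sided drift, which nothing in the documents shows. A reader might also infer that the estimated difference itself is imprecise. Under close matching it is about as precise as the adjusted estimate; what is lost is the accuracy of the reported standard error, and with it power.

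**Conclusion.** The point holds as a conditional improvement to the analysis rather than a fatal flaw. The omission is plain from the documents; its size is not. If the four variables explain 10% to 30% of outcome variance beyond speed, the reported standard error of level comparisons is 5% to 20% too wide, and adjustment would raise power at 0.5 SD from about 60% to between 64% and 75%. If they explain nothing, there is no loss.

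The direction of the error in the false-positive rate depends on how the matching turns out: below 5% when differences balance, and up to about 9% in the worst one-sided case examined at R2 = 0.3. These figures rest on the assumed R2, effect size, covariate SDs and equal weights, and should be read as a range rather than a forecast. The suggestion is worth considering because the downside is very small.

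**What to change.** Add one sentence to the SAP: sex, age, body mass and running experience will be covariates in the between-group models, alongside those already listed.

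This works whether matching is by pairs or by group averages, and it keeps participants whose match drops out. A pair term would suit only one-to-one matching, would leave 80 - 40 - 2 = 38 degrees of freedom instead of 73, and would lose a whole pair when one member is missing.

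No new data are needed, because matching already requires all four variables. The cost is four degrees of freedom (77 to 73; critical t 1.991 to 1.993). If the variables predict nothing, power at 0.5 SD goes from 59.8% to 59.7% under close pairwise matching, and falls by about 1 point if only group means are matched.

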## Procedures

### *Recruitment and screening*

Volunteers will be recruited via print and social media, as well as advertisements in local running clinics. We will also contact individuals from our database of previous study participants and screening individuals who have expressed interest in future studies and provided explicit consent to be contacted again. Interested volunteers will be screened via phone, email, or our lab website by the study coordinator to assess inclusion and exclusion criteria. Individuals passing initial screening will sign a detailed consent form. They will then receive a copy of the MRI Screening Form to assess MRI safety criteria. Those who pass will then be referred to have standing, semi-flexed postero-anterior radiographs of both of their knees taken. A trained assessor will grade all radiographs based on the KL criteria. Those who pass all screening for their respective group will be enrolled.

### *Data collection*

Two separate time points will be included for both biomechanics and MRI testing: baseline and follow-up, with identical protocols at all time points.

a) Biomechanics testing – This will be conducted using high-speed motion analysis cameras and an instrumented treadmill. A total of 42 reflective markers (31 lower limb, 11 upper limb) will be affixed to the skin bilaterally over key anatomical landmarks as is standard in our laboratory. Participants will run on the treadmill for 30 minutes at a self-selected speed. We will collect synchronized kinematic (sampled at 200 Hz) and kinetic (2000 Hz) data for 15 seconds at the start of the run, as well as after 10, 20, and 30 minutes of running. Participant averages for each outcome will be calculated across these time points, as is commonly done in the biomechanics literature. For safety reasons, we will assess knee pain at these time points as well, and will cease the run if pain exceeds 7/10 on a numerical rating scale – common for running studies in the presence of pain. In the event of a stopped run, another assessment will be scheduled and MRI testing will be postponed.

b) MRI testing – Baseline MRI data collection will occur one week following biomechanics testing. Upon arriving at the centre, participants will complete activity questionnaires to assess physical activity levels, as well as the Knee Osteoarthritis Outcome Score (KOOS) to characterize knee symptoms. When combined with study instruction briefing, this will ensure that participants remain seated and inactive for 30 minutes prior to scanning.

Next, participants will undergo the first MRI of the **study knee** [defined as the arthritic knee (unilateral OA) or the most symptomatic knee (in cases of bilateral OA) in the TFOA group; randomly chosen in the Control group] on a research-dedicated Philips 3.0 Tesla MRI scanner. The protocol will include T2 and T1ρ mapping sequences, as well as anatomical scans to assess joint orientation and cartilage integrity. Including participant preparation, each full block of scans lasts approximately 30 minutes in duration.

Following the pre-run MRI, participants will complete a single bout of treadmill running for 30 minutes in their own shoes. To control for the potential effect of running speed on results, participants will choose a comfortable speed between 6 and 10 km/h.

After running for 30 minutes, participants will run back to the MRI scanner for an immediate post-run MRI assessment.

#### *Running intervention*

Participants will receive a 12-week running program under the model of building up to a 10 km race. Three weekly training sessions will be planned, and mileage will gradually increase by an average of 10% per week as we have done in our recent running studies. For the purpose of this study, participants will run using their habitual technique – i.e. no specific instructions on ‘how’ to run will be provided at this stage; rather, they will simply be instructed on ‘how much’ to run. A Study Trainer not involved in any aspect of data collection or analysis will oversee the implementation of the intervention via weekly phone conversations with participants to ensure proper adherence and to prescribe appropriate weekly mileage increases. Participants will be provided with a GPS-enabled wrist watch to record their running distance throughout the intervention, which will be supplemented with weekly self-report logs completed online.

#### *Data processing and analysis*

MR images will be segmented and analyzed by a collaborator who has previous experience working with our group. This collaborator will be blinded to group and to whether the scan was performed before or after the 12-week running program.

Motion analysis data will be processed and analyzed by a trained student. Though data will be collected bilaterally, analysis of biomechanics data for the purposes of this study will be constrained to the study

limb, consistent with all other outcomes.

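### The MRI reader's stated blinding omits scan time within a session, so the planned test of the acute effect of running is not stated to be protected from reader bias

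*Protocol*

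**What the plan says.** The Protocol's Study design section sets out "to obtain direct and indirect measures of the effects of running on knee cartilage in people with and without TFOA". Under Data collection, the MRI visit has a scan, a run and another scan: "Following the pre-run MRI, participants will complete a single bout of treadmill running for 30 minutes in their own shoes", after which "participants will run back to the MRI scanner for an immediate post-run MRI assessment".

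Under Data processing and analysis, one person produces the imaging outcome: "MR images will be segmented and analyzed by a collaborator who has previous experience working with our group". The blinding rule follows directly: "This collaborator will be blinded to group and to whether the scan was performed before or after the 12-week running program". It has two items, group and programme period.

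The SAP plans a group by scan-time repeated measures ANCOVA at each MRI session, to look at group differences and at "changes across the MRI scan times (pre-run, immediate-post, 45-minute-post), and any interactions present". It uses p = 0.05 without multiplicity correction, with the reason: "To account for the exploratory nature of this research".

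Two other statements concern independence. The Protocol (Running intervention) keeps the Study Trainer out of data collection and analysis, and the SAP makes the statistician independent. Neither person segments images.

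**The concern.** The rule masks the reader to the slower contrast (before or after 12 weeks) but is silent on the faster one (before or after 30 minutes of running). The faster one is a planned test in its own right, because the scan-time main effect is the acute effect of running on T2 and T1ρ.

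That test compares each person with themselves. Pairing removes much of the between-person variation, so a small systematic difference in how known pre-run and post-run images are segmented can be large relative to the standard error. Such a shift adds directly to the estimated acute change, and recruiting more participants does not reduce it.

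**Working it through.** **Step 1: the text.** Contrasts that the SAP tests on MRI outcomes, against the blinding that the Protocol states for the reader:

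| Contrast | Masking stated for the reader? |
|---|---|
| Group | Yes |
| Before/after the 12-week programme | Yes |
| Scan time within a session | Not mentioned |
| Group by scan time | Group yes, scan time not mentioned |

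The second item of the rule refers to the 12-week programme and cannot be read as referring to the treadmill run. No section describes coded files, hidden acquisition times or reading order. The SAP lists three scan times, while the Protocol's Data collection section describes a pre-run and an immediate post-run scan. The gap is the same under either count.

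**Step 2: which tests a shift would reach.** Let a reader who knows scan order add a shift d_T to post-run values in the TFOA group and d_C in the Control group.

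- Acute change within a group: true change + d_T (or + d_C). Exposed.
- Scan-time main effect: true average change + (d_T + d_C)/2. Exposed.
- Group by scan-time interaction: true difference in change + (d_T − d_C). Unaffected only if d_T = d_C.
- Programme contrast: covered by the stated blinding.

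**Step 3: an illustration of size.** There is no plan figure to reproduce: the Protocol gives no sample size calculation, and neither document gives an SD, a correlation or a reader error.

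- From the documents: 80 participants (40 per group) and a 0.05 significance level.
- Assumed: all 80 complete; two-sided test; equal SD at each scan; pre/post correlation r from 0.5 to 0.95; no true acute effect; covariates ignored; shift d in SD units, the same in both groups.

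For two scan times, SE of the mean paired change = √(2(1 − r)/80):

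- r = 0.5: √(1.0/80) = 0.112 SD
- r = 0.8: √(0.4/80) = 0.071 SD
- r = 0.95: √(0.1/80) = 0.035 SD

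The noncentrality is d/SE. For example, d = 0.05 gives 0.05/0.112 = 0.447 at r = 0.5, and 1.414 at r = 0.95 (unrounded SE). Noncentral t with 78 df gives these false-positive rates for the scan-time effect:

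| Shift d | r = 0.5 | r = 0.8 | r = 0.95 |
|---|---|---|---|
| 0.01 SD | 0.051 | 0.052 | 0.059 |
| 0.02 SD | 0.054 | 0.059 | 0.086 |
| 0.05 SD | 0.073 | 0.108 | 0.287 |
| 0.10 SD | 0.143 | 0.287 | 0.798 |

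**Step 4: sensitivity.**

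- Three scan times, the same shift on both post-run scans, compound symmetry: the shift vector (0, d, d) has sum of squares about its mean of (2/3)d², so λ = 80 × (2/3)d²/(1 − r), with 2 and 156 df. The rates are 7-28% for d = 0.05 and 14-83% for d = 0.10.
- 64 completers (an assumed 20% loss: 80 × 0.8), two scan times, 62 df: 7-24% for d = 0.05 and 12-70% for d = 0.10.
- Simulation of 20,000 trials, two scan times, common shift 0.10 SD, r = 0.5, 0.8 and 0.95: scan-time rejection 0.148, 0.290 and 0.800, in line with the last row of the table. Interaction rejection was 0.051, 0.050 and 0.049, in line with step 2.

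**The case against.** The strongest reply is that this is silence, not a stated flaw. Hiding programme period already implies some handling of dates or labels, and the same handling may hide scan time. That may be so, and a reader should not infer that the collaborator is unblinded to scan order: no section says it. What stands is that the rule names two items, and compliance with both leaves scan order open.

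Second, the mechanism is unknown. The documents do not say whether segmentation is manual, semi-automated, or done once and carried over to the other scans in a session. If contours are carried over, a reader-driven shift between scans could be small. This stands. It is why bias can be called possible and no more, and why a random reading order cannot be required without knowing the workflow.

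Third, the figures rest wholly on assumed shifts and correlations. This also stands. With shifts of 0.01-0.02 SD the rate barely leaves 5%, and the largest figures need a 0.10 SD shift together with r = 0.95.

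Fourth, the study's emphasis is on comparing groups, and the SAP calls the work exploratory. The first part narrows the exposure, since a shift common to both groups cancels from the interaction. The second lowers the stakes of any single nominal result. But the SAP offers the exploratory label as its reason for not correcting for multiplicity, which is a matter of chance findings. A systematic shift is not chance.

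**Conclusion.** The point holds as a gap in the stated rule. The reader's blinding covers group and programme period but not scan time within a session, and scan time is a tested factor at each MRI session. The exposed quantities are the scan-time main effect and the within-group acute changes. The interaction is safe only under an equal shift in both groups; blinding to group makes an unequal shift less likely but does not rule it out.

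A reader might go further and conclude that the acute results will be biased, or that the trial's false-positive rate will be as high as 80%. The documents support neither. Under the step 3 assumptions the rate runs from close to nominal (about 5-9% at 0.01-0.02 SD) through 7-29% at 0.05 SD to 14-80% at 0.10 SD. Nothing in the documents says where in that range this trial would lie. The case for acting is that the protection is cheap and the contrast is planned, not that harm has been shown.

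**What to change.** In the Protocol, Data processing and analysis, extend the rule to: *blinded to group, to session (before/after the programme) and to scan time within session*.

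To carry it out, give each scan a code and mask acquisition times and any label that reveals scan time or session. Keep the key from the reader until segmentation is complete. Sequence type (T2, T1ρ, anatomical) can stay visible. Read scans in random order where the segmentation workflow allows it. If scan time is already masked in practice, the added wording is enough.

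The cost is a small amount of file recoding, with no added scan or reader. It is best done before reading starts, because scans already read with their order known could be fully protected only by re-reading them.
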